5.2 Contraception Recommendations

Contraception Requirements for Females

Participants must follow the following contraceptive guidelines as specified:

Females do not need to use birth control during or following study drug treatment if considered of non-childbearing potential due to meeting any of the following criteria:

- Postmenopausal, age > 55 years with no menses for 12 or more months without an alternative medical cause.
- Postmenopausal, age ≤ 55 years with no menses for 12 or more months without an alternative medical cause AND a follicle-stimulating hormone (FSH) level > 30 IU/L.

- Permanently surgically sterile (bilateral oophorectomy, bilateral salpingectomy, or hysterectomy).

Females of childbearing potential must avoid pregnancy while taking study drug and for at least 30 days after the last dose of study drug.

Females must commit to one of the following methods of birth control:

- Combined (estrogen and progestogen containing) hormonal birth control (oral, intravaginal, transdermal, injectable) associated with inhibition of ovulation initiated at least 1 month prior to Screening.
- Progestogen-only hormonal birth control (oral, injectable, implantable) associated with inhibition of ovulation initiated at least 1 month prior to Screening.
- Bilateral tubal occlusion/ligation, i.e., Essure (can be via hysteroscopy, provided a hysterosalpingogram confirms success of the procedure).
- Intrauterine device (IUD).
- Intrauterine hormone-releasing system (IUS).
- Vasectomized sexual partner (provided the vasectomized partner has received medical confirmation of the surgical success of the vasectomy and is the sole sexual partner of the trial participant).
- Practice true abstinence, defined as: Refraining from heterosexual intercourse when this is in line with the preferred and usual lifestyle of the participant (periodic abstinence [e.g., calendar, ovulation, symptothermal, post-ovulation methods] and withdrawal are not acceptable).

Contraception Requirements for Males

For males who may participate in the study, the following methods of contraception, if properly used, are generally considered reliable: postbilateral vasectomy, barrier contraception, or sexual abstinence. Contraception should be used while taking study drug and for at least 30 days after the last dose of study drug.

Male participants must also refrain from donating sperm during the course of the study for at least 30 days after the last dose of study drug.

5.3 Prohibited Medications and Therapy

- Strong/moderate CYP3A4 inducers, including but not limited to: barbiturates (e.g., phenobarbital and primidone), systemic (oral/intravenous [IV]) glucocorticoids (e.g., methylprednisolone, prednisolone, prednisone), nevirapine, efavirenz, pioglitazone, carbamazepine, phenytoin, rifampin, rifabutin, and St. John's Wort.
- Usage of opioids > 4 days/month in the 3 months prior to Screening, or during the screening/baseline period.

- Strong CYP3A4 inhibitors, including but not limited to: systemic (oral/IV) itraconazole, ketoconazole, clarithromycin, telithromycin, nefazodone, and HIV protease inhibitors.
- Oral medications with demonstrated efficacy for the prevention of migraine (e.g., amitriptyline, propranolol).
- Use of oral gepants (e.g., Ubrelvy™, Nurtec™) for acute or preventive migraine treatment.
- Injectable mAbs blocking the CGRP pathway (e.g., Aimovig™, Emgality™, Ajovy®, Vyepti™).
- New use of cannabinoids (i.e., marijuana), or cannabidiol (CBD) oil (systemically used) during study.
- Current use of **any** botulinum toxin (any serotype, therapeutic or cosmetic), regardless of location apart from BOTOX for migraine treatment.
- Grapefruit or grapefruit juice from the time the consent form is signed until completion of the study. Participants should also refrain from making significant changes to their diet or caffeine intake during the study.
- A non-exhaustive list of prohibited medications can be found in the Operations Manual, Section 7.1 ([Appendix F](#)).

5.4 Prior and Concomitant Therapy

Any medication or vaccine (including over-the-counter or prescription medicines, vitamins, and/or herbal supplements) that the participant is receiving at the time of enrollment or receives during the study must be recorded from 4 weeks prior to study drug administration through the post-treatment visit (Week 28).

Any questions regarding concomitant or prior therapy should be raised to the AbbVie emergency contact. Information regarding potential drug interactions with atogepant or with BOTOX can be located in the atogepant Investigator's Brochure and the BOTOX USPI.

Participants must be able to safely discontinue any prohibited medications 5 half-lives or 4 weeks prior to initial study drug administration. Participants must be consented for the study prior to discontinuing any prohibited medications for the purpose of meeting study eligibility.

For the acute treatment of migraine, the following medications are allowed during the study:

- Any triptan
- Any ditan
- Any ergot derivative
- Any opioid (≤ 4 days per month)
- Any other form of analgesic (including acetaminophen)
- Any NSAID agent
- Any antiemetic agent

5.5 Withdrawal of Participants and Discontinuation of Study

A participant may voluntarily withdraw or be withdrawn from the study at any time for reasons including, but not limited to, the following:

- Clinically significant abnormal laboratory results or AEs, which rule out continuation of the study drug, as determined by the investigator or the sponsor.
- The investigator believes it is in the best interest of the participant.
- The participant requests withdrawal from the study.
- Eligibility criteria violation was noted after the participant started study drug and continuation of the study drug would place the participant at risk.
- Introduction of prohibited medications or dosages and continuation of the study drug would place the participant at risk.
- The participant becomes pregnant while on study drug.
- Participant is significantly noncompliant with study procedures, which would put the participant at risk for continued participation in the trial.

A subject must be permanently discontinued from the study if any of the following criteria are met:

- The subject experiences any serious AE of hypersensitivity or anaphylactic reaction.
- The subject experiences a nonserious AE of hypersensitivity unless there is clear alternative etiology.

For participants to be considered lost to follow-up, reasonable attempts must be made to obtain information on the participant's final status. At a minimum, 2 telephone calls must be made and 1 certified letter must be sent and documented in the participant's source documentation.

AbbVie may terminate this study prematurely, either in its entirety or at any site. The investigator may also stop the study at his/her site if he/she has safety concerns. If AbbVie terminates the study for safety reasons, AbbVie will promptly notify the investigator.

5.6 Follow-Up After Participant Discontinuation of Study Drug or from Study

To minimize missing data for efficacy and safety assessments, participants who prematurely discontinue study drug treatment should continue to be followed for all regularly scheduled visits, unless participants have decided to discontinue the study participation entirely (withdrawal of informed consent). Participants should be advised on the continued scientific importance of their data even if they discontinue treatment with study drug early.

If a participant prematurely discontinues study participation (withdrawal of informed consent), the procedures outlined for the Premature Discontinuation visit (PD visit) should be completed as soon as

possible, preferably within 2 weeks. In addition, if participant is willing, a 30-day follow-up phone call after the last dose of study drug may be completed to ensure all treatment-emergent AEs/SAEs have been resolved.

In the event a participant withdraws consent from the clinical study, biomarker research will continue unless the participant explicitly requests analysis to be stopped. When AbbVie is informed the participant has withdrawn and no longer wishes biomarker samples research to continue, samples will not be analyzed and no new biomarker analysis data will be collected for the withdrawn participant or added to the existing data or database(s). A participant may withdraw consent for optional biomarker research at any time and remain in the clinical study. Data generated from clinical study and/or optional biomarker research, before participant withdrawal of consent, will remain part of the study results.

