 INTERVIEW	
 Review concomitant medications and procedures 	
 Adverse events eDiary return visit
 PRO	
 Review eDiary data and compliance C-SSRS PROMIS v2.0 Cognitive Function Abilities Short-Form 6a MSQ v2.1 PHQ-9 	
 GAD-7 WPAI:MIGRAINE PSSM PGIC Complete headache assessments via eDiary (daily) AIM-D eDiary return
 EXAM	
 ECG Physical examination 	
 Collect vital sign measurements (vital sign measurements: sitting BP and pulse rate, respiratory rate, temperature, weight)
 LAB	
 Urine pregnancy test 	
 CENTRAL LAB	
 Collect clinical laboratory samples Optional biomarker collection for CGRP (saliva and plasma) 	
 Lipid profile, marker of inflammation, adipokine hormones, HbA1c
 TREATMENT	
 Completion of atogepant dosing 	
 Administer BOTOX injection (concomitant medication), \pm 7 days

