3.7 Biomarker Research Sampling

Biospecimens (whole blood and saliva) will be collected to support the biomarker research objectives of the study. Please refer to the Study Activities Schedule in Appendix D for the schedule of biomarker research sample collections. Assessments may include, but are not limited to, biomarkers related to the pathway(s) targeted by the study drug, or those believed to be related to the disease(s) being studied. The information learned from analyzing these samples may be used to investigate factors influencing response to treatment, scientific questions related to chronic migraine, and/or in the development of new therapies and diagnostic tests.

DNA/RNA isolated from whole blood may be analyzed to determine specific genetic mutations in patients with migraine and related conditions as well as determine if any of these mutations are associated with response to treatment with BOTOX and/or atogepant (or drugs of this class). In addition, plasma and saliva may be analyzed to determine concentrations of calcitonin gene-related peptide (CGRP) or related neuropeptides to determine if changes in these peptides are related to migraine or associated with response to treatment with BOTOX and/or atogepant (or drugs of this class).

All biomarker samples should be labeled and shipped as outlined in the study-specific laboratory manual. AbbVie (or people or companies working with AbbVie) will store the samples and data in a secure storage space with measures to protect confidentiality. The samples may be retained while research on atogepant and/or onabotulinumtoxinA (BOTOX) (or drugs of this class) or migraine and related conditions continues, but for no longer than 20 years after study completion, or per local requirement.

3.8 12-Lead Electrocardiogram

12 Lead Electrocardiogram (Single Only)

Resting 12-lead electrocardiogram (ECG) will be obtained singly as specified in Appendix D of the study protocol.

The ECG acquired prior to atogepant dosing will serve as the baseline measurements for clinical assessment.

When an ECG is scheduled at the same time as a blood collection, the ECG will be obtained prior to the blood collection. ECGs occurring near meals will take place prior to meals.

ECGs will be acquired after the participant has been in the supine position for at least 5 minutes. Participants will be instructed to remain completely stationary (no talking, laughing, deep breathing,

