3.14 Participant Withdrawal from Study

All attempts must be made to determine the date of the last study drug dose and the primary reason for discontinuation of study drug or study participation. The information will be recorded on the appropriate eCRF page. However, these procedures should not interfere with the initiation of any new treatments or therapeutic modalities that the investigator feels are necessary to treat the participant's condition. Following discontinuation of study drug, the participant will be treated in accordance with the investigator's best clinical judgment, irrespective of whether the participant decides to continue participation in the study.

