10.2.1 Treatment-Emergent Adverse Events

Treatment-emergent AEs (TEAEs) are defined as any AE with the onset that is after the first dose of study drug. Events when the onset date is the same as the study drug start date are assumed to be treatment-emergent. An AE that occurs more than 30 days after the last dose of open-label study treatment will not be counted as a TEAE. All TEAE will be summarized overall, as well as by primary MedDRA SOC and PT. The SOC will be presented in alphabetical order, and the PTs will be presented in alphabetical order within each SOC.

The number and percentage of participants experiencing TEAEs will be summarized.

An AE will be considered a treatment-emergent serious AE (TESAE) if it is a TEAE that additionally meets any SAE criterion.

TEAEs that started after the date of last dose of study treatment will be considered as newly emergent.

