10.5 Other Safety Analyses

10.5.1 Electrocardiogram

Descriptive statistics for ECG parameters (i.e., heart rate, PR interval, QRS interval, RR interval, QT interval, and QTc interval) at baseline, postbaseline, and changes from baseline values at each postbaseline timepoint will be presented.

ECG parameter values are considered PCS if ECG values meet either the actual value or change from baseline PCS high criteria listed in Table D-4. The number and percentage of

participants with PCS postbaseline values and postbaseline values of clinical interest listed in Table D-5 will be tabulated. The number and percentage of participants with PCS postbaseline values will be summarized. The percentages will be calculated relative to the number of participants with an available non-PCS baseline value and at least 1 postbaseline assessment. The numerator will be the total number of participants with an available non-PCS baseline value and at least 1 PCS postbaseline ECG value during the study. A supportive listing of participants with PCS postbaseline values will be provided. A listing of all AEs for participants with PCS ECG values will also be provided.

A shift table from baseline to the end of open-label treatment period in the overall interpretation of the ECG will be presented for the following categories: normal and abnormal. A tabular display of participants with postbaseline clinically significant ECG abnormalities according to the investigator's overall interpretation will be provided.

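### Minor: participants who stop atogepant early have no scheduled on-drug post-baseline ECG, the PD visit is stated only for consent withdrawal, and SAP 10.5.1 counts ECGs however long after the last dose

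*Protocol*

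**What the plan says.** - **Follow-up after stopping drug.** Protocol 5.6: "participants who prematurely discontinue study drug treatment should continue to be followed for all regularly scheduled visits". Operations Manual 3.14 also separates stopping drug from leaving the study, and has sites record "the date of the last study drug dose and the primary reason for discontinuation of study drug or study participation".
- **PD visit.** The same section continues: "If a participant prematurely discontinues study participation (withdrawal of informed consent), the procedures outlined for the Premature Discontinuation visit (PD visit" are to be completed promptly. Consent withdrawal is the only trigger given. Protocol 5.5 lists other ways out: adverse events or laboratory results, the investigator's judgement, and mandatory discontinuation from the study for hypersensitivity.
- **ECG schedule.** Operations Manual 3.8: "Resting 12-lead electrocardiogram (ECG) will be obtained singly as specified in Appendix D of the study protocol". Appendix D and the Operations Manual 2.1 visit lists place an ECG at Visit 2 and at Visit 8, where the treatment entry reads "Completion of atogepant dosing". Visits 3 to 7 have none. The one early-termination column in Appendix D is shared with Visit 9 and has no ECG.
- **ECG analysis.** SAP 10.5.1 counts participants with a non-PCS baseline and "at least 1 PCS postbaseline ECG value during the study". The denominator requires at least one post-baseline assessment. The SAP also plans "A shift table from baseline to the end of open-label treatment period in the overall interpretation of the ECG".
- **Adverse events, by contrast.** SAP 10.2.1: "An AE that occurs more than 30 days after the last dose of open-label study treatment will not be counted as a TEAE".

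**The concern.** Safety is the primary objective and ECG is a listed safety endpoint. Two groups of early stoppers are handled loosely.

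Participants who stop only atogepant are kept in the study, which is right for the diary and for most safety data. Their one scheduled post-baseline ECG, however, may be taken months after the last dose. It then enters the PCS percentage, and probably the end-of-treatment shift table, on the same footing as an ECG taken on drug. A normal tracing well after stopping says little about the drug but still enlarges the denominator.

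Participants withdrawn from the study under 5.5 have no PD visit stated for them in 5.6, and the procedures that 5.6 describes as outlined do not appear in the site schedules. A participant who leaves without a post-baseline ECG drops out of the SAP 10.5.1 denominator altogether.

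The gap is not confined to ECG. The post-baseline physical examination and the lipid, inflammation-marker, adipokine and HbA1c panel are also scheduled only at Visit 8.

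**Working it through.** **1. The plan's own figures (Protocol 7.7).** 20% of 75 = 15 early terminations, leaving 60. Chance of at least one event of 4% incidence in 75 participants: 1 − 0.96^75 = 95.3%, against 95% stated. Both reproduce, and neither is in dispute.

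**2. Time off drug at the Week 24 ECG.** For a participant who stops only atogepant, this is 24 minus the stop week:

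| Stop week | 4 | 6 | 8 | 12 | 16 | 20 |
|---|---|---|---|---|---|---|
| Weeks off drug | 20 | 18 | 16 | 12 | 8 | 4 |

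Scheduled on-drug post-baseline ECGs in every case: 0.

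**3. How many ECGs fall beyond 30 days.** The documents do not split early terminations into drug-only stoppers and study leavers, so the range used is 0 to 15. Assume stop times uniform over 168 days. The mean gap to Week 24 is 168/2 = 84 days (12 weeks), and the share beyond 30 days is (168 − 30)/168 = 82.1%. That gives 4.1, 8.2 or 12.3 ECGs for 5, 10 or 15 drug-only stoppers, and none if there are no such participants.

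**4. Scale only.** Suppose an off-drug ECG cannot show a drug effect, and borrow the 4% incidence that 7.7 uses for AEs:

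| On-drug ECGs | Chance of at least one event, 1 − 0.96^n | Incidence seen with 95% probability, 1 − 0.05^(1/n) |
|---|---|---|
| 75 | 95.3% | 3.9% |
| 70 | 94.3% | 4.2% |
| 65 | 93.0% | 4.5% |
| 60 | 91.4% | 4.9% |

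**5. PD content, document by document.** Appendix D has no PD column. Operations Manual 2.1 and 2.2 have no PD entry. Operations Manual 6.1 names a PD visit as the alternative to the end of treatment, but only for contacting the IRT system and returning drug. SAP 2.2 pairs PD with Visit 8, which includes an ECG; sites do not work from the SAP. The intent can be inferred, but the site instruction is not written.

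**6. A fallback ECG at the next scheduled visit.** Both visits carry a ±3-day window. Visit 3 can fall on Day 29 − 3 = 26 and Visit 4 on Day 57 + 3 = 60, so the gap can reach 60 − 26 = 34 days. Such an ECG may therefore also miss a 30-day limit.

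**The case against.** The strongest reply is that one end-of-treatment ECG is a reasonable choice for an approved drug. The documents name no cardiac or QT signal, and both AESIs are hepatic. Participants who stay in the study have laboratory tests and vital signs at every treatment visit, and AEs are collected for at least 30 days after the last dose. All of that stands, and it keeps the point minor.

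A reader might infer that participants withdrawn under 5.5 will have no post-baseline ECG. The documents do not show this. SAP 2.2 and Operations Manual 6.1 make a PD visit with Visit 8 content likely. Operations Manual 3.8 uses the local ECG reading for AE management and decisions to discontinue, which fits ECGs taken when clinically needed. For the same reason it cannot be said that those who stop for AEs are especially unlikely to have an ECG near the last dose.

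A reader might also take 95.3% to 91.4% as a loss of planned power. It is not one: the 4% target concerns AEs, no ECG target exists, and 60 on-drug ECGs is the extreme case. The figure also assumes that off-drug ECGs carry no information. A fallback ECG at the next visit would be off drug too, so the table cannot be read as what that ECG would recover.

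Finally, SAP 10.3 counts hepatic laboratory values at any time during the study, so a 30-day split for ECG alone departs from that convention. This is a real cost of the fix. It does not make an ECG taken 18 weeks after the last dose an on-treatment result.

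**Conclusion.** The point holds as a minor one. As scheduled, a drug-only stopper has no on-drug post-baseline ECG, and SAP 10.5.1 does not separate the Week 24 tracing by time since last dose. The stated PD trigger in 5.6 is narrower than the withdrawals allowed in 5.5, and PD procedures are absent from the site schedules.

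The number affected is unknown, from 0 to about 15 of 75 on the plan's 20% early termination. At that ceiling, with uniform stop times, about 12 ECGs would be read more than 30 days after the last dose. No stated design figure fails. The conclusion rests on Appendix D and the Operations Manual visit lists; unscheduled ECGs are neither required nor excluded.

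**What to change.** 1. **Protocol 5.6, Appendix D and Operations Manual 2.1.** Apply the PD visit to anyone who leaves the study early for any reason, including withdrawals under 5.5. Add a PD column and a PD visit entry with the Visit 8 safety assessments, without BOTOX. Drug-only stoppers stay on their regular visits.
2. **SAP 10.5.1.** For study leavers, use the PD ECG as the end-of-treatment ECG. Report ECGs taken more than 30 days after the last atogepant dose separately from the on-treatment PCS and shift summaries. Last-dose dates are already recorded (Operations Manual 3.14), so this needs no new data.
3. **Optional.** For drug-only stoppers, take an ECG at the time of stopping or, failing that, at the next scheduled visit, up to 34 days later. This is an extra procedure for 0 to about 15 participants, and the fallback may still fall outside 30 days.

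Cost: wording changes, a few more PD assessments, a slightly smaller on-treatment ECG denominator, and a window that differs from the SAP's hepatic laboratory summaries.

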5.7 Study Drug

Atogepant manufactured by AbbVie will be taken orally with or without food once daily (QD) beginning on Day 1 and should be taken at approximately the same time each day. If participants should forget to take their atogepant dose at their regularly scheduled dosing time, they should take the forgotten dose as soon as they remember, and then take their next dose at the regularly scheduled dosing time.

Participant dosing will be recorded on the eCRF. The study site personnel will document compliance.

AbbVie will provide study drug for atogepant. AbbVie provided study drug should not be substituted or alternately sourced unless otherwise directed by AbbVie.

Atogepant will be packaged in bottles with quantities sufficient to accommodate study design. Each kit will be labeled per local requirements and this label must remain affixed to the kit. Upon receipt, study drug should be stored as specified on the label and kept in a secure location at the site. Each kit will contain a unique kit number. This kit number is assigned to a participant via interactive response technology (IRT) and encodes the appropriate study drug to be dispensed at the participant's corresponding study visit. Site staff will complete all blank spaces on the label before dispensing to participants. Study drug will only be used for the conduct of this study.

